### **6.3. Derived and Transformed Data**

#### **6.3.1. Study Day**

If the date of interest occurs on or after the date of first dose, Study Day will be calculated as (date of interest – date of first dose) + 1.

If the date of interest occurs before the date of first dose, Study Day will be calculated as (date of interest – date of first dose).

There is no Study Day 0. For analysis, Day 1 is defined as the day of the first study drug dose. The preceding day is Day -1.

### **6.3.2. Age**

Only year of birth is captured in the clinical database. Hence, for analysis purposes, each subject's age at enrollment into Study 0171 is not derived but set to their age in integer years as reported by the site.

### **6.3.3. Change from Baseline**

Change from baseline is calculated as postbaseline result – baseline result. If either the baseline or the postbaseline result is missing, change values are treated as missing.

### **6.3.4. BMI (Body Mass Index)**

BMI is calculated as:

$$BMI (kg / m^2) = \frac{weight (kg)}{height (m)^2}.$$

BMI will be calculated using height as collected in Study 0169 or Study 0170 and weight as collected at Study 0170 Visit 9 (Day 154)/Study 0171 Visit 1 (Day -1).

### **6.3.5. Visit Windows**

All assessments will be summarized using analysis windows. The term “out of window” will be applied to assessments that are outside the analysis windows, regardless of the visit label associated with the assessment in the EDC system.

The following visit windows will be used in the summarization of clinical data:

**Table 4: Analysis Windows**

Nominal Visit	Analysis Window	
	Start (days)	Stop (days)
Baseline	See Section 6.2.	
Week 2 (Day 14)	7	21
Week 6 (Day 42)	35	49
Week 10 (Day 70)	63	77
Week 14 (Day 98)	91	105
Week 18 (Day 126)	119	133
Week 22 (Day 154)	147	161
Week 26 (Day 182)	175	189

#### 6.3.6. Multiple Assessments

In general, if multiple valid observations exist at a visit or collection time point, the record(s) to be included in the summary and analyses will be chosen based on the following:

- The record closest to the nominal time

If 2 records are equidistant or distance cannot be determined:

- The later record

If there are 2 or more records with the same date/time:

- The average (generally applies to assessments done in triplicate)

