#### **6.4.3.6. Vital Signs**

The HR, BP, RR, and body temperature will be recorded according to the Schedule of Study Procedures ([Table 1](#)).

The vital sign measurements (BP and HR) should be performed after the subject has rested sufficiently as determined by the appropriate staff. Subject position, measurement device, and arm (left vs. right) should be kept consistent throughout the study. Blood pressure will be measured using a calibrated manual or automatic BP device.

Heart rate will be recorded by palpation of the radial pulse over at least a 30-second period or by the automated BP device.

Body temperature will be measured and reported in degrees Celsius. The method used to collect temperature can be either oral or tympanic but should be consistent throughout the subject's participation.

Any vital sign outside the normal range may be repeated at the discretion of the Investigator. Collection of additional vital sign measurements for routine safety monitoring at additional time points or study days may be performed at the discretion of the Investigator, or upon request by the sponsor.

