### 8.4.2. [REDACTED]

## 8.5. Safety Analyses

For all safety analyses, the safety set will be used.

Safety variables to be summarized include vital signs, adverse events, clinical laboratory results (hematology, chemistry, and urinalysis), corrected QT interval (QTcF) from standard safety digital ECGs and C-SSRS. Vital signs, ECGs and laboratory results will be summarized in terms of observed values and changes from baseline.

Summaries will be provided by nominal visit and time point or for the entire treatment period, as appropriate for the type of data. Quantitative data collected at unscheduled times will be listed but will not be included in summaries. Categorical data collected at unscheduled times (e.g., ECG finding categories) will not be included in summaries by time point but will be included in summaries of findings during the entire treatment period.

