#### 8.5. Vital Signs

Vital sign (HR, systolic and diastolic BP, respiratory rate, and body temperature) values and their changes from baseline at each visit will be summarized. If baseline BP and HR were collected as a part of the orthostatic standing test at Visit 9 (Day 155) in Study 0170, the seated values will be used to calculate the change from baseline. The counts and percentages of subjects with vital signs in the following categories will be presented in a vital signs extreme values summary. Extreme values will be flagged in the listing.

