## 8.8. Columbia-Suicide Severity Rating Scale (C-SSRS)

The C-SSRS is a tool designed to systematically assess and track suicidal AEs (suicidal behavior and suicidal ideation). The strength of this suicide classification system is in its ability to comprehensively identify suicidal events while limiting the over-identification of suicidal behavior. The C-SSRS Since Last Visit Version will be used in this study.

The following 11 C-SSRS categories include 5 subtypes of suicidal ideation (1–5), 5 subtypes of suicidal behavior (6–10), and self-injurious behavior without suicidal intent. They all have binary responses (yes/no).

1. Wish to be Dead
2. Non-specific Active Suicidal Thoughts
3. Active Suicidal Ideation with Any Methods (Not Plan) without Intent to Act
4. Active Suicidal Ideation with Some Intent to Act, without Specific Plan
5. Active Suicidal Ideation with Specific Plan and Intent
6. Preparatory Acts or Behavior
7. Aborted Attempt
8. Interrupted Attempt
9. Actual Attempt (non-fatal)
10. Completed Suicide
11. Self-injurious Behavior Without Suicidal Intent

Frequency counts and percentages will be presented for subjects in each C-SSRS category, as well as subjects with any suicidal ideation (1–5), subjects with any suicidal behavior (6–10), and subjects with any suicidal ideation or behavior (1–10), by visit at which the items were collected.

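### The one-record-per-visit rule in SAP 6.3.6 lets a repeat displace a valid out-of-threshold reading, so the extreme-values table can undercount affected subjects; it can also drop a positive C-SSRS form

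*SAP*

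**What the plan says.** SAP 6.3.6 covers visits with more than one valid observation. It opens with a general qualifier, then says "the record(s) to be included in the summary and analyses will be chosen based on the following". First choice is "The record closest to the nominal time". "If 2 records are equidistant or distance cannot be determined", the later record is taken. Records with identical date and time are averaged, which the SAP says is meant mainly for triplicates.

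The windows in SAP Table 4 are in whole days, seven either side of the nominal day. SAP 6 makes unscheduled records inside a window eligible for summaries.

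Protocol 6.4.3.6: "Any vital sign outside the normal range may be repeated at the discretion of the Investigator". Protocol 6.4.3.9.4 allows unscheduled visits with any protocol assessment.

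SAP 8.5: "The counts and percentages of subjects with vital signs in the following categories will be presented in a vital signs extreme values summary" (Table 5 sets SBP > 160 or < 85 mmHg, among others). It does not say whether all readings or only the selected one are counted. SAP 8.8 counts C-SSRS categories "by visit at which the items were collected", using the Since Last Visit form, with no whole-period row.

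**The concern.** Picking one record by timing is reasonable for a mean or a change from baseline. It suits a threshold count poorly, because the second reading may exist only because the first was abnormal. If the repeat falls back inside the limit, the subject leaves the row that the table exists to report.

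The C-SSRS problem differs in kind. Each form covers the interval since the previous one. A later negative form therefore does not contradict an earlier positive one, yet the rule treats the two as competing measurements of one moment.

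Vital signs and the C-SSRS are primary safety endpoints of this single-arm study, so the tabulated percentages are what readers will use.

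**Working it through.** The plan gives no outlier rate or expected loss, so there is no stated figure to reproduce.

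**Step 1: the rule applied literally (Week 10, nominal Day 70, window Days 63–77, SBP threshold > 160).** Readings are illustrative.

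| Records | Value used | Counted > 160? | Any reading > 160? |
|---|---|---|---|
| Day 70 09:00, 172; Day 70 09:20, 150 | 150 | no | yes |
| Day 70, 172; Day 71, 150 | 172 | yes | yes |
| Day 68, 172; Day 71, 150 (closer) | 150 | no | yes |
| Day 68, 172; Day 72, 150 (tie, later) | 150 | no | yes |
| Same date/time, 172 and 150 | 161 | yes | yes |
| Same date/time, 165 and 150 | 157.5 | no | yes |

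The first row infers that two readings on one day are tied because Table 4 counts in days. A repeat on another day displaces the first reading only if it is closer, or tied and later.

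**Step 2: direction.** The value used is either one of the records or their average. It cannot exceed 160 unless at least one record does, and the same argument holds for the low limits. For each subject and visit, the Table 5 count is therefore at most the any-reading count.

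**Step 3: size, on assumptions only.** None of these inputs is in the documents: true SBP T ~ N(μ, 15²) with μ = 135 or 145; readings A and B given T independent N(T, s²) with s = 6, 8 or 12; every first reading above a trigger c repeated once the same day and replaced by the repeat. No normal range is given for vital signs, so c is taken as 160, 150 or 140.

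Let g(T) = P(A > 160 | T) and h(T) = P(A > c | T). Then:

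- First readings above 160: F = E[g].
- Values used above 160: U = E[h·g], since with c ≤ 160 this needs A > c and B > 160.
- Any reading above 160: Y = E[g] + E[(h − g)·g].
- Net loss against first readings = 1 − U/F. Shortfall against any reading = 1 − U/Y.

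Numerical integration gives these extremes of the grid:

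| Trigger | μ, s | F | U | Y | 1 − U/F | 1 − U/Y |
|---|---|---|---|---|---|---|
| > 160 | 145, 6 | 17.66% | 12.22% | 17.66% | 31% | 31% |
| > 160 | 135, 12 | 9.66% | 3.79% | 9.66% | 61% | 61% |
| > 150 | 145, 6 | 17.66% | 16.63% | 22.07% | 6% | 25% |
| > 150 | 135, 12 | 9.66% | 6.17% | 12.03% | 36% | 49% |
| > 140 | 145, 6 | 17.66% | 17.59% | 23.03% | 0.4% | 24% |
| > 140 | 135, 12 | 9.66% | 8.10% | 13.96% | 16% | 42% |

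If only half of the triggering readings are repeated, 1 − U/F halves. The net loss shrinks with a lower trigger because a reading of, say, 152 may be repeated at 164 and add an outlier. The last column stays larger because each repeat also gives a further chance of a high reading.

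**Step 4: C-SSRS.** Suppose an unscheduled form on Day 67 records ideation and the scheduled Day 70 form is negative since that contact. Both lie in Days 63–77. Day 70 is at distance 0 and Day 67 at distance 3, so the negative form is kept and the subject is not counted at Week 10.

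**The case against.** The strongest reply is that the rule is blind to values. A reader might infer that it always removes abnormal findings and never normal ones. That is not so: an abnormal unscheduled reading on Day 70 displaces a normal scheduled one on Day 66, and a repeat triggered below 160 can itself exceed 160. What stands is narrower: the table can never exceed the any-reading count and can fall short of it.

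A reader might also infer that raised blood pressure is then visible only in listings. The documents say otherwise. Supine hypertension is an AESI, asked about at each visit (Protocol 7.1.4), with its own summary (SAP 8.1.1). Clinically significant abnormal findings that meet the AE definition are recorded as AEs (Protocol 7.2). Extreme vital signs are flagged in the listing.

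Nor did the SAP clearly remove a protection that the protocol gave Table 5. Protocol 8.5 says that unscheduled categorical data "will be included in summaries of findings during the entire treatment period", but it gives ECG finding categories as the example and keeps unscheduled quantitative data out of summaries.

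The case is weaker beyond vital signs and the C-SSRS. SAP 10.2.4 uses a laboratory retest when the first result is invalid, which suggests that a valid first result stands. Protocol 6.4.3.7 does not prompt a repeat because an ECG was abnormal, and averaging triplicates is the protocol's own rule (8.5.6).

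Finally, 6.3.6 is a general rule; 8.5 does not say that Table 5 is by visit; 8.8 might be read as its own rule; and clock times for vital signs may not be stored. These points leave room for an exception, but none is written. SAP 6.3.5 applies windows to all assessments, and averaging also loses some outliers.

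**Conclusion.** The concern holds for Table 5 and the C-SSRS. As written, a valid out-of-threshold vital sign can be replaced or averaged away by a same-day repeat, and a positive C-SSRS form can be dropped for a negative one nearer the nominal day. That a same-day repeat counts as the later record of a tie is an inference from day-based windows.

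The size cannot be derived from the documents. The 31–61% range is tempting as the headline but applies only if repeats start exactly at the Table 5 limit and every such reading is repeated. With lower triggers the net loss is 6–36% (> 150) or 0.4–16% (> 140), and it halves if half are repeated. The loss is confined to these tables; listings, AE tables and the AESI table retain part of the signal. The change should be made, but the point does not call the safety database into question.

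**What to change.** - Limit the single-record rule in SAP 6.3.6 to continuous by-visit summaries.
- **Table 5:** count a subject under each threshold, high and low separately, if any valid post-baseline on-treatment record (scheduled, unscheduled or repeat) crosses it. Show this by window and in an any-time-on-treatment row.
- **Table 6:** apply the same rule after averaging each ECG triplicate. State the averaging explicitly: replicates are timed at least a minute apart, so 6.3.6 read literally would keep only the last one.
- **Laboratory shifts:** take worst-high and worst-low separately.
- **C-SSRS:** count any positive response in the window and add an any-time-on-treatment row.
- Exclude invalid readings, and define the on-treatment period for these rows.

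The cost is a few sentences in the SAP and some programming flags before database lock, with no new data. The downside is that some transient readings will be counted, so outlier percentages become slightly less favourable. Any-reading counts also rise with the number of readings taken, which a table footnote should say.

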#### **6.4.3.7. Electrocardiograms**

The 12-lead ECGs will be recorded in triplicate and separated by at least 1 minute for each replicate, according to the Schedule of Study Procedures ([Table 1](#)), after the subject has been resting at least 5 minutes in the seated or supine position before the first reading. Actual time of the assessment must be recorded for each iteration. The corrected QT interval using the Fridericia's formula (QTcF) will be used. The ECGs should be reviewed on the visit day at the site to allow for any appropriate action, if required.

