**Table 4: Electrocardiogram Test Outlier Thresholds**

Heart Rate (bpm)	Heart Rate Change From Baseline (bpm)	PR Interval (msec)	PR Percentage Change From Baseline (%)	QRS Interval (msec)	QT c F (msec)	QT c F Change From Baseline (msec)
>120	≥20	≥200	≥15	≥120	Males:	≤30
>130	≥30	≥220	≥25		<430	>30, ≤60
					≥430	>60
					≥450	
					≥470	
					≥480	
					≥500	
					Females:	
					<450	
					≥450	
					≥470	
					≥480	
					≥500	

Treatment emergent ECG abnormalities are defined as those not present at baseline, or those that worsened after treatment, e.g., borderline at baseline but were prolonged after treatment. QTcF {and QTcB} will also be summarized by the following categories, Normal (males <430, females <450), Borderline (males (≥430, <450); females (≥450, <470)) and Prolonged (males ≥450, females ≥470).

When multiple values exist for the same nominal time point (e.g., triplicate reading), the average of the readings taken for ECG parameters will be used in the data analysis, including the outlier analysis stated below.

Subjects without post-baseline measurement for a given treatment period will be excluded from the summary statistic (e.g., denominator of the summary statistic) for that time point.

All recorded values for the ECG parameters will be presented in a by-subject listing. A separate listing of subjects with values of QTcF > 500 msec or an increase > 60 msec will be provided, as necessary.

Cumulative distribution plots will be provided for maximum change in QTcF by day.

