- Study drug will be ingested in the morning at approximately the same time of day with 8 ounces of water. The exact time and day of dosing will be recorded on the mornings of study visits. Subjects must be reminded to maintain an adequate fluid intake during their scheduled visits. Subjects will start taking study drug on the day after Visit 1.
- ECGs are done in triplicate after the subject has been resting for at least 5 minutes in a seated or supine position before the first reading, with each replicate separated by at least 1 minute.

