### **8.2. Extent of Exposure and Treatment Compliance**

Duration of study drug exposure (days) will be summarized. Duration of exposure to study drug is calculated as (date of last dose – date of first dose + 1).

Subjects will take their assigned study medication once daily.

Treatment compliance as a percentage of the expected total dose will be calculated as follows, using the information captured on the CRF page for “Study Drug Dispensing / Return”:

$$100 \times \frac{\text{(number of tablets dispensed – number returned)}}{\text{(date of last dose – date of first dose + 1)}}$$

Treatment compliance as a percentage of expected total dose over the interval from first to last dose will be summarized as a continuous variable and using the following categories, after rounding to the nearest 0.1%:

- $\geq 120\%$
- $\geq 80\% - < 120\%$
- $< 80\%$

Study drug administration (date/time and study day) and drug accountability data will be listed.

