### 10.2.2. Missing Start and Stop Dates for Adverse Events

Missing start date and times will be handled as follows:

- AE onset date completely missing:
  - If AE is not ongoing and AE onset date missing and AE end date missing, then impute AE onset as date/time of first dose.
  - Else if AE is not ongoing and AE onset date missing and AE end date not missing and date/time of first dose  $\leq$  AE end date, then impute AE onset as date/time of first dose of study drug.
  - Else if AE is not ongoing and AE onset date missing and AE end date not missing and AE end date is BEFORE first dose of study drug, then impute AE onset as AE end date YEAR and MONTH with 01 as the day and 00:00 as time.
  - Else if AE IS ongoing and AE onset date missing, then impute AE onset as date/time of first study drug dose.
- AE onset date has year and month only:
  - If AE onset date has year and month only and they are the year and month of first dose of study drug, then impute AE onset as date/time of first dose:
  - Else if AE onset date has year and month only and date/time of first dose is not missing, then impute AE onset as AE onset year and month with 01 as the date and 00:00 as the time.
- AE onset date has year only:
  - If AE onset date has year only and it is year of first dose of study drug, then impute AE onset as date/time of first dose of study drug.
  - Else if AE onset date has year only and date of first study drug dose is not missing and year of AE onset is NOT the year of first dose of study drug, then impute AE onset as Jan. 1 of the AE onset year and 00:00 as the time.
- AE onset missing (where it was not handled by the above cases):

- If AE onset date is missing, then impute AE onset as date/time of first study drug dose.
- AE onset has complete date but missing time:
  - If AE onset date is a date only and is same as date of first study drug dose, then impute AE onset as date/time of first study drug dose.
  - Else if AE onset date is a date only and is NOT = date of first study drug dose, then impute AE onset as AE onset date with 00:00 as the time.

Missing end date and times will be handled as follows:

- AE end date - completely missing:
  - If AE is not ongoing and both AE onset and AE end dates are missing, then impute AE end date as date/time of last study drug dose.

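### Does the SAP's trigger for averaging repeated records shut out the individually timed ECG triplicates it is meant for?

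*SAP*

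**What the plan says.** SAP Section 6.3.6 gives three steps for multiple valid observations at a visit or collection time point. The first keeps the record nearest the nominal time. The second, introduced by "If 2 records are equidistant or distance cannot be determined", keeps the later record. The third, introduced by "If there are 2 or more records with the same date/time", prescribes "The average (generally applies to assessments done in triplicate".

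The ECG procedure is described elsewhere. The ECG footnote to SAP Table 2 calls for triplicates "with each replicate separated by at least 1 minute". Protocol Section 6.4.3.7 has the same spacing and adds "Actual time of the assessment must be recorded for each iteration".

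Protocol Section 8.5.6 has its own averaging rule, which opens "When multiple values exist for the same nominal time point (e.g., triplicate reading), the average of the readings taken for ECG parameters" and goes on to apply that average in the data analysis and in the outlier analysis. SAP Section 8.6, which defines the ECG summaries and the Table 6 categories, does not repeat the rule.

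**The concern.** Three readings taken at least a minute apart, each with its own recorded time, do not share a date and time in the clock sense. On that reading the averaging step fails for exactly the assessments its bracketed remark names. The SAP does use clock time in other places: Section 8.2 states "Study drug administration (date/time and study day) and drug accountability data will be listed", and Section 10.2.2 has a separate case headed "AE onset has complete date but missing time".

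If averaging is out of reach, the nearest remaining step is the later-record rule. A programmer working from the SAP alone might then keep only the last replicate. Resting ECG is a primary safety endpoint, so the QTcF, PR, QRS, QT and heart rate summaries, and the category counts in SAP Table 6, would rest on single readings and be noisier than the protocol intends. Baseline looks exposed too: SAP Table 4 gives it no nominal day, and SAP Section 6.2 does not say how a triplicate becomes one value. Baseline enters every change score.

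**Working it through.** The plan states no figure to reproduce here, so the main check is to apply the rules to a concrete case: replicates timed 10:00, 10:01 and 10:02 on the same day.

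1. **Clock time.** The three stamps differ, so the averaging trigger is false. The later-record step does not fit cleanly either, because it is worded for two records and there are three. Taken strictly, the text leaves a gap here. It does not direct the use of one replicate.

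2. **Day level.** SAP Table 4 gives nominal times only as days (Week 10 is Day 70, Week 26 is Day 182). All three replicates are equally far from the nominal day, so the first step ties. None falls on a later day, so the second step ties. They share a date, so the third step applies and they are averaged. The steps work as a chain of tie-breaks that ends where the bracketed remark says it should.

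3. **Mixed reading.** To reach the last replicate, distance must be measured in days, *later* must be judged by the clock, and a rule written for two records must be stretched to three. The averaging step would then apply to no triplicate collected as the protocol requires.

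4. **Protocol against SAP.** Protocol Section 8.5.6 keys averaging to a shared nominal time point, which the three replicates meet on any reading. Protocol Section 8.1 says that changes to protocol-specified analyses will be pre-specified in the SAP, and the visible SAP declares none for this rule. The two documents prescribe the same analysis.

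5. **Baseline.** SAP Section 6.2 chooses which assessment serves as baseline. Reducing the triplicate within that assessment falls to Protocol Section 8.5.6 and to the SAP's remark on triplicates, as at any other visit.

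6. **Size if single readings were used anyway.** The documents give no QTcF variance components, so this is an illustration. Let sv be the visit-to-visit SD and sr the replicate SD, with nb and np replicates used at baseline and post-baseline and no true change:

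   SD(change) = √(2·sv² + sr²/nb + sr²/np); expected count = 110 × [1 − Φ(30/SD)].

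   The 110 is the number enrolled (SAP Section 2), an upper bound at any visit. With sv = sr = 8 msec (assumed):

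   | Replicates used (nb, np) | SD of change (msec) | P(change > 30) | Expected of 110 |
   |---|---|---|---|
   | 3, 3 | √170.67 = 13.06 | 0.0108 | 1.2 |
   | 3, 1 | √213.33 = 14.61 | 0.0200 | 2.2 |
   | 1, 1 | √256 = 16.00 | 0.0304 | 3.3 |

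   For sv from 6 to 12 and sr from 5 to 10, the excess over averaging is 0.1 to 1.9 subjects with a single reading post-baseline only, and 0.3 to 3.7 with single readings at both visits. A noisier case, sr = 12 with sv = 8, gives 7.8 against 2.5 with single readings at both visits. Over the first of these ranges, the count above 60 msec is at most 0.36 against 0.08.

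**The case for a change.** The best case for a change is that a programmer codes from the SAP. The trigger phrase does not match the timed records, the SAP uses date and time in the clock sense elsewhere, and the later-record step comes before averaging. One sentence stating that replicates are averaged first, with the other rules then choosing between separate sets, would remove all doubt at almost no cost.

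Part of this stands. The phrase is imprecise, and the protocol's wording is cleaner. The rest carries less weight. The passages on drug administration and adverse event onset list data items or impute times; neither defines how ECG records are compared. The order of the steps does no harm at day level, because no replicate is later than another. A programmer who did meet a gap has the remark on triplicates in the same step and the explicit ECG rule in the protocol, and both give the same answer.

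Two things cannot be settled from the visible text. One is whether Study 0170 baseline ECGs reach this database as three records or as one mean. The other is whether redacted SAP text adds a further rule. Neither gives a reason to expect single readings.

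**Conclusion.** This is a clerical looseness that analysts will resolve correctly. Averaging is plainly intended, the protocol requires it for the ECG parameters, and the SAP steps arrive at it when records are compared by day. Rewording the trigger would leave every planned ECG summary as it is.

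The modelled counts show what a literal program could do under assumed SDs; they are not a consequence of the plan. Even then the summaries are descriptive, no test depends on them, the extra replicate noise would not bias mean changes, and every reading stays in the listings. The conclusion rests on two assumptions: that the protocol rule still holds, as no departure is visible, and that ECG is the only assessment taken in triplicate, as the visible schedules show.
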